## ALLOB-DU1 - Clinical Study Protocol

ALLOB-DU1\_CSP

V 05

Author: [name]

February 02, 2017

Pg. 5/136

**ALLOB-DU1 - Clinical Study Protocol**

ALLOB-DU1\_CSP

V 05

Author: [name]

February 02, 2017

Pg. 10/136

**STUDY SYNOPSIS****EudraCT Number:** 2012-005333-36**Protocol Number:** 000005/BT**Protocol Code:** ALLOB-DU1**Sponsor or Sponsor's representative in the European Union**

Bone Therapeutics S.A., Gosselies, Belgium

**Phase of Development**

Pilot Phase I/IIa Study

**Planned Study Period**

Total recruitment period: until maximum 32 patients have been treated

Total study follow-up period: 6 months

**Objectives**

To evaluate the safety and efficacy of ALLOB®, a proprietary population of allogeneic osteoblastic cells, in the treatment of delayed-union fractures of long bones, given as single percutaneous administration directly into the delayed-union site.

**Planned Number of Subjects:**

Maximum 35 enrolled patients for maximum 32 treated patients (assuming 10 % drop-out). A minimum of 16 completed patients is required for the Interim Analysis.

**Medical Condition, Patient Selection and Inclusion Criteria**

Men and women, aged 18 to 80 years old, diagnosed with a non-infected delayed-union fracture of a long bone (femur, tibia, fibula, humerus, ulna and radius) of minimum 3 ( $\pm$  2 weeks) and maximum 7 months ( $\pm$  2 weeks) at the time of inclusion.

**ALLOB-DU1 - Clinical Study Protocol**

ALLOB-DU1\_CSP

V 05

Author: [name]

February 02, 2017

Pg. 11/136

**Test procedure, product, dose and mode of administration**

ALLOB® is an allogeneic osteoblastic cell product falling under the EMA classification EMA/486246/2011 as tissue engineered Advanced Therapy Medicinal Products (ATMP).

ALLOB® will be given percutaneously as a single administration into the delayed-union site using a trephine. The volume administered is based on the size of the delayed-union gap and determined as follow:

Fracture interline < 0.5 cm: 2 ml of suspension solution

Fracture interline  $\geq$  0.5 –  $\leq$  1 cm: 3 ml of suspension solution

Fracture interline > 1 –  $\leq$  2.5 cm: 4 ml of suspension solution

In case implantation using 2 surgical sites is judged best approach by the investigator, a total of up to 4 ml may be administered.

**Detailed visit schedule**

After informed consent is obtained, fulfilment of study inclusion and exclusion criteria will be performed at Visit #1, which will take up to 8 weeks to complete. Visit #2 is scheduled to take place after completion of Visit #1 for baseline clinical assessments and ALLOB® implantation (the baseline of the radiological assessments is Visit #1). At Visit #2, all patients will be hospitalized for 24 or 48 hours after implantation, according to the judgment of the Investigator.

Patients will be followed during 6 months, at 2 weeks, 1, 3, and 6 months (Visit #3 to Visit #6).

[REDACTED]

[REDACTED]

[REDACTED]

[REDACTED]

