## 2 INVESTIGATIONAL PLAN

### 2.1 General Study Design

The present study is a prospective, multicentre, open, non-controlled study to assess the safety and efficacy of allogeneic osteoblastic cells (ALLOB®) implantation in non-infected delayed-union fractures.

After signing the Informed Consent Form (ICF), enrolled patients will enter an up to 8 weeks screening period. Eligible patients (according to the eligibility criteria) will be treated by a single ALLOB® implantation into the delayed-union site. Once treated, patients will be followed up during 6 months with post-treatment assessments performed: at 2 weeks, 1, 3 and 6 months, respectively. During follow-up, non-responding patients (see below and section 3.2.3) could be considered as drop-out and undergo a rescue surgery, according to the judgment of the Investigator.

[REDACTED]

[REDACTED]

[REDACTED]

Experimental design	Prospective, multicentre, open, non-controlled Phase I/IIa study
Duration of study	6 months of follow-up
Delayed-union sites	Femur, tibia, fibula, humerus, ulna, radius
Treatment	ALLOB ®
Procedure	Implantation performed under anaesthesia
Study Timepoints	2 weeks, 1 month, 3 months and 6 months after treatment

Self-contained study

Data collection: Case Report Form (CRF)

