#### *Duration of delayed-union*

As the trial involves patients diagnosed with delayed-union fractures of a long bone (see 2.4.1) at the time of inclusion, and as the time between screening and implantation could take up to 8 weeks, delayed-union patients could be screened (Visit #1) as from a fracture duration of 3

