**ALLOB-DU1 - Clinical Study Protocol**

ALLOB-DU1_CSP	V 05	Author: [name]	February 02, 2017	Pg. 50/136
---------------	------	-------------	-------------------	------------

global view of the fracture and will improve the assessment. Numerous studies have expounded the benefits of computed tomography in providing a more accurate assessment of healing and a higher correlation with fracture rigidity (Morshed *et al.*, 2008). One study showed good reliability and diagnostic accuracy of CT for tibial non-union fractures ( $\kappa = 0.67$ ,  $p < 0.0001$ ; sensitivity = 100%, specificity = 62%), versus plain radiography ( $\kappa = 0.14$ ,  $p = 0.36$ ; sensitivity = 54%, specificity = 62%) (Bhattacharyya *et al.*, 2006).

In this pilot phase I/IIa study, the primary target for TUS as assessed by CT scan will be an improvement of at least 2 points at Month 6, as an improvement by two points of TUS means:

- There is a total consolidation of one cortices, or
- There is a bone union on two cortices (even if the fracture interline is still visible), or
- The disappearance of the fracture interlines on two cortices in bone union.

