## 5 DETAILED DESCRIPTION OF THE PROCEDURES

### 5.1 Revision Procedure prior to the Trial

Osteosynthesis revision or surgery of the delayed-union under study is allowed prior to entry into the study:

- If there is a minimum of 2 months between the revision/surgery and the screening if the revision/surgery has been performed at the fracture site
- If there is a minimum of 4 weeks between the revision/surgery and the screening if the revision/surgery has been performed outside the fracture site.

At screening (Visit #1), the absence of signs of radiological healing (due to the osteosynthesis revision performed before the study) will be confirmed by the Independent Radiologist. This will be done by comparing conventional X-Ray (and/or CT scan) performed at screening Visit #1 with the X-Ray (and/or CT scan) performed before the study (min. time of 4 weeks).

Upon the Independent Radiologist or the Principal Investigator's judgement as needed (e.g., absence or poor quality of pre-study images, pre-study images whose dates are too close from the dates of the fractures...), a second set of X-ray can be performed during screening period (i.e., 4 weeks after the first set of X-rays), in order to assess the evolution of the fracture: absence of fracture healing over the last 4 weeks at time of inclusion (inclusion criterion, section 2.6.2).

However, all efforts must be done to collect the images performed at the time of revision.

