#### **10.5.6 Efficacy analysis**

##### **10.5.6.1 Primary efficacy criteria**

The primary efficacy criteria will be analysed in the safety population and in the PP population, the safety population corresponding to the main efficacy population.

Percentage of responder patients will be calculated as the percentage of patients who will not be considered as failed under treatment at Month 6.

A patient will be considered as failed under a treatment if, at Month 6:

- He/she had a rescue surgery

Or

- The Global Disease Evaluation score (VAS) as perceived by the patient has not improved by at least 25% *and* the TUS as assessed by CT scan has not increased by at least two points (versus baseline).

[REDACTED]

[REDACTED]

[REDACTED]

[REDACTED]

[REDACTED]

ALLOB-DU1 - Clinical Study Protocol

ALLOB-DU1 CSP

V 05

Author: [name]

February 02, 2017

Pg. 100/136

A series of horizontal black bars of varying lengths, likely representing a redacted list of items. The bars are arranged vertically and have irregular, jagged ends, suggesting they are cut-off fragments of a larger list. The lengths of the bars vary significantly, with some being very short and others being quite long.

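### The TUS baseline is taken in screening rather than at implantation, so a point gained before treatment can count toward the +2-point success criterion

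*Combined protocol and SAP*

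**What the plan says.** The two components of the primary endpoint have different starting points.

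- **Radiological baseline.** The synopsis (Detailed visit schedule) says that "the baseline of the radiological assessments is Visit #1".
- **Clinical baseline.** The same paragraph says that "Visit #2 is scheduled to take place after completion of Visit #1 for baseline clinical assessments" and for implantation. The Global Disease Evaluation (GDE) is therefore measured from the day of treatment.
- **Length of the gap.** The synopsis describes "Visit #1, which will take up to 8 weeks to complete". Section 2.1 says that "enrolled patients will enter an up to 8 weeks screening period", and section 2.6.1 that "the time between screening and implantation could take up to 8 weeks".
- **Use of the TUS.** Section 3.2.2 says that "the primary target for TUS as assessed by CT scan will be an improvement of at least 2 points at Month 6". Under section 10.5.6.1, a patient without rescue surgery fails only if the GDE has not improved by 25% and, in addition, "the TUS as assessed by CT scan has not increased by at least two points (versus baseline".
- **Checks for absence of healing.** Section 2.6.2 requires no signs of healing over the 4 weeks up to screening. Sections 2.6.1 and 5.1 compare Visit #1 images with pre-study images. Section 5.1 adds that, on judgement, "a second set of X-ray can be performed during screening period".

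**The concern.** The TUS change is meant to measure the effect of the implanted product. With the baseline CT in screening, it also includes whatever happened between that CT and implantation. Section 1.1.1 describes delayed union as slow healing that is expected to finish without intervention, so some change in that time is plausible.

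No control arm would share this drift. The success rate is compared with a fixed 30% (section 10.5.8.2), so a patient who reaches +2 points only with the help of pre-treatment change is counted as a treatment success. The error favours the product.

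**Working it through.** **Step 1. Is TUS alone enough?** For a patient without rescue surgery, under sections 2.2.2, 10.2 and 10.5.6.1:

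| GDE improved by 25% or more | TUS up by 2 or more | Result |
|---|---|---|
| yes | yes | success |
| yes | no | success |
| no | yes | success |
| no | no | failure |

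The third row shows that a TUS gain can create a success by itself.

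**Step 2. How long can the gap be?** The stated maximum is 8 weeks. Visit #6 is at 24 ± 3 weeks (section 4.7), so the TUS window is at most 8 + 24 = 32 weeks, or 35 at the late limit. Up to 8/32 = 25% of the calendar window is then before treatment. With a 4-week gap the share is 4/28 = 14%, and with 2 weeks it is 2/26 = 8%.

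The maximum is not open to everyone. Section 2.6.1 limits screening to 7 months and treatment to 8 months after fracture, each ± 2 weeks. A patient screened at 7 months has 8 − 7 = 1 month, about 4 weeks, or about 6 if the 2-week tolerance on treatment is used.

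**Step 3. Do the checks cover the gap?** The inclusion criterion looks back 4 weeks from screening. The radiologist's confirmation compares Visit #1 images with older ones. Both end at Visit #1. The second X-ray set, 4 weeks after the first, would cover part of the gap when it is used. It is optional, it serves eligibility, it is not a CT, and the text does not say that it replaces the CT baseline. The readable text contains no repeat CT at Visit #2.

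**Step 4. What can a pre-treatment change supply?** By Annex 4, the TUS is the sum of four cortex scores, each a whole number from 0 to 4. The smallest gain is 1 point, which is 1/2 = 50% of the threshold. Two such steps before implantation would meet it in full.

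**Step 5. What would this do to decisions?** The plan gives no figure for this. As an illustration only, let q be the share of true failures who reach +2 solely because of pre-treatment change. A true rate of 30% then appears as 0.30 + 0.70q. The values of q are assumptions. The probabilities are exact binomial.

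| q | 0 | 5% | 10% | 20% |
|---|---|---|---|---|
| Apparent success rate | 0.300 | 0.335 | 0.370 | 0.440 |
| P(12 or more of 16), efficacy stop | 0.0003 | 0.0008 | 0.0023 | 0.0121 |
| P(fewer than 4 of 16), futility as in the text of 2.5 and 10.5.8.3 | 0.25 | 0.16 | 0.10 | 0.03 |
| P(4 or fewer of 16), futility as in the table of 10.5.8.3 | 0.45 | 0.33 | 0.24 | 0.10 |
| P(15 or more of 32), assumed final rule | 0.033 | 0.081 | 0.165 | 0.438 |

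The last row uses a single-stage exact 5% rule, because the plan shows n.a. for both limits at the second stage. The planned sample size does not enter this point.

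**The case against.** The case on the other side is substantial.

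- **The real gap cannot be read.** Visit #1 is a period, not a date. The visit schedule and the procedures for Visits #1 and #2 are redacted, so the CT may already fall late in screening. This stands: 8 weeks is a ceiling, not the typical gap.
- **Patients enter as non-progressing.** Someone with no healing over 4 weeks must then gain a whole cortex grade in the next few weeks to benefit. This makes the event less likely but does not rule it out.
- **The one explicit efficacy boundary hardly moves.** Even at an assumed q of 20%, the chance of 12 or more successes out of 16 under a true 30% is about 1%. This stands. The effect falls on the futility stop and on any final comparison with 30%.
- **The SAP may deal with it.** Section 10 defers to a separate SAP that is not in the text available, and what follows the primary criterion in section 10.5.6.1 is redacted. An omission from the SAP therefore cannot be shown.

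A reader might also draw two stronger conclusions that the documents do not support. The first is that up to a quarter of the TUS gain itself precedes treatment. The 25% is a maximum share of calendar time. Turning it into points assumes steady healing and produces fractional gains that an integer score cannot show. The second is that recent osteosynthesis revision is known to drive healing inside the gap. Sections 2.6.1 and 5.1 set two minimum intervals before screening, 2 months for revision at the fracture site and 4 weeks for revision elsewhere. They also require the Independent Radiologist to confirm that no such healing is visible.

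**Conclusion.** The point holds as a weakness in how the primary endpoint is anchored. The protocol explicitly starts the TUS change at Visit #1 and the GDE change at implantation. It lets up to 8 weeks pass between screening and implantation, and no mandatory check covers that time. A whole-point TUS gain in the gap is credited to the product, and +2 points alone makes a success in the absence of rescue surgery.

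The direction of the bias is clear, but its size is not. The documents give neither the CT-to-implantation interval nor a rate of TUS change in screening, so the table under Step 5 shows sensitivity and is not an estimate. The conclusion assumes that the redacted schedule sets no short CT-to-implantation window. If it does, only the reporting part of the remedy remains. The correction is inexpensive and worth making, but the point does not by itself invalidate the trial's decision rule.

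**What to change.** **Protocol.** Book the existing baseline CT late in screening, once the X-ray and other eligibility checks are met. State a maximum CT-to-implantation interval, chosen by the sponsor, unless the redacted schedule already sets one. This is workable because the entry score is mainly the X-ray mRUS, with TUS used only when mRUS cannot be assessed (section 2.6.2 and its footnote).

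**SAP.** Report the CT-to-implantation interval for every treated patient. Add a sensitivity analysis of the primary success rate in which patients beyond the stated interval cannot succeed on TUS alone, or are excluded. With at most 32 patients this will be descriptive.

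**Cost.** Protocol wording and tighter scheduling of a scan that is already planned. Any eligibility item that depends on CT is known later in screening. If implantation slips, the patient falls outside the window. The sensitivity analysis should handle that case, not a repeat CT.

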**Duration of treatment**

This is a single dose administration study.

## ALLOB-DU1 - Clinical Study Protocol

ALLOB-DU1_CSP	V 05	Author: [name]	February 02, 2017	Pg. 12/136
---------------	------	-------------	-------------------	------------

**Patient Inclusion Scheme:**

In order to maximise patient safety, for the first 16 patients treated, patient recruitment will proceed stepwise by blocks of 4. Full first 2 weeks safety data of the first block of 4 treated patients will be analysed before the first patient of the second block of 4 is treated. First 48 hours safety data of the second block of 4 treated patients will be analysed before treatment of the first patient of the next block. This latter scheme will be repeated until 16 patients have been treated. This review of reported SAE potentially related to the Investigational Medicinal Product (IMP), and especially those related to immunological reactions (severe Adverse Event of Special Consideration (AESc)), will be done by the Safety Monitoring Committee (SMC).

**Study Endpoints and Criteria for Evaluation****Safety Criteria**

In addition to standard pharmacovigilance requirements, particular attention will be given to AE suggesting immune-mediated reactions, such as: general discomfort, uneasiness, ill feeling, pain or swelling in the implanted area, fever and any inflammatory reactions, flu-like symptoms (e.g., chills, body aches, shortness of breath, cutaneous rashes...). All severe AEs potentially related to the IMP and in particular those potentially related to the allogeneic reactions will be managed by the SMC who will analyse and report these events in a timely manner consistent with the safety of patient recruitment scheme.

**Efficacy Criteria**

The following clinical and radiological criteria will be used:

- Clinical: Global disease evaluation (GDE) score as assessed by the patient and Investigator using a Visual Analogue Scale (VAS); Pain using a VAS; Weight-bearing score using a Likert Scale
- Radiological healing progression as assessed by CT scan and by conventional X-ray using the Tomographic Union Score (TUS) and modified Radiological Union Score (mRUS), respectively

**ALLOB-DU1 - Clinical Study Protocol**

ALLOB-DU1\_CSP

V 05

Author: [name]

February 02, 2017

Pg. 13/136

**Evaluation Time Points**

Efficacy and safety endpoints will be determined at each scheduled visit over the 6-month follow-up period (at 2 weeks, 1, 3 and 6 months).

The interim report and the decision for continuation will be established on the first 16 assessable patients after 6 months of follow-up and the final Clinical Study Report (CSR) will be established at 6 months (end of study) after treatment for all patients, as applicable.

**Interim Analysis**

A Data Safety Monitoring Board (DSMB) will be established to analyse and report the safety and the efficacy data when 6-month post-treatment results from the first 16 assessable patients will be available. This Board will recommend whether to continue, modify or stop the study. If success is less than 30% or higher than 70%, patient recruitment will be stopped. If the DSMB recommendation is continuation (with or without changes) of the study, patient recruitment will continue until 32 patients have been treated.

**Statistical Analysis**

Statistical methods will be exhaustively described in a Statistical Analysis Plan (SAP), which will constitute the only reference document. The SAP will be reviewed, approved, and signed prior to database lock at the latest.

The safety population will be considered as the primary cohort for analysis of efficacy. It will comprise all treated patients.

***Efficacy Endpoints:***

The efficacy of ALLOB® will be evaluated at 6 months. The success will be based on the percentage of treated patients (ALLOB®) not failing under treatment. A treated patient will be considered as failed if, at the end of the study (6 months):

ALLOB-DU1 - Clinical Study Protocol

ALLOB-DU1 CSP

V 05

Author: [name]

February 02, 2017

Pg. 14/136

- The patient had required a rescue surgery or
- The Global Disease Evaluation score as perceived by the patient has not improved by at least 25% *and* the TUS as assessed by CT scan has not increased by at least 2 points.

All safety analyses will be conducted on the safety population and tabulated. For each AE and SAEs reported, the number and percentage of patients will be tabulated based on system organ class and preferred term. Similar tabulations will be performed by severity, relationship to the

**ALLOB-DU1 - Clinical Study Protocol**

ALLOB-DU1_CSP	V 05	Author: [name]	February 02, 2017	Pg. 15/136
---------------	------	-------------	-------------------	------------

study product/procedure, action taken and outcome. The frequency of AEs and SAEs will be assessed using a 95% Confidence Interval.

More details will be given in the SAP.

**Ethical considerations**

This study will be conducted in accordance with applicable laws and regulations including, but not limited to, the International Conference on Harmonisation (ICH) Guideline for Good Clinical Practice (GCP) and the ethical principles that have their origins in the Declaration of Helsinki. The Institutional Review Board (IRB)/Independent Ethics Committee (IEC) must review and approve the protocol and the Informed Consent Form (ICF) before any patients are enrolled. Before any protocol-required procedures are performed, the subject must sign and date the IRB/IEC-approved ICF.

**Date and Version of the Study Protocol: 02 Feb 2017, V05**

## ALLOB-DU1 - Clinical Study Protocol

ALLOB-DU1_CSP	V 05	Author: [name]	February 02, 2017	Pg. 16/136
---------------	------	-------------	-------------------	------------

## ALLOB-DU1 - Clinical Study Protocol

ALLOB-DU1_CSP	V 05	Author: [name]	February 02, 2017	Pg. 17/136
---------------	------	-------------	-------------------	------------

## LIST OF ABBREVIATIONS

ADR	Adverse Drug Reaction
AE	Adverse Event
AESC	Adverse Event of Special Consideration
AST	Aspartate Amino Transferase (also known as:
(SGOT)	Serum Glutamic-Oxaloacetic Transaminase)
ALT	Alanine aminotransferase (also known as:
(SGPT)	Serum Glutamic-Pyruvic Transaminase)
ATMP	Advanced Therapy Medicinal Product
BMI	Body Mass Index
BP	Blood Pressure
CAs	Competent Authorities
CAT	Committee for Advanced Therapies (EMA)
CBMP	Cell-Based Medicinal Products
CHMP	Committee for Medicinal Product for Human Use (EMA)
CI	Confidence Interval
CMV	Cytomegalovirus
CPMP	Committee for Proprietary Medicinal Products (EMA)
CRA	Clinical Research Associate
CRF/eCRF	Case Report Form/electronic Case Report Form
CRO	Contract Research Organization
CSR	Clinical Study Report
CT	Computed Tomography
CTA	Clinical Trial Application
CU	Clinical Unit
DCF	Data Clarification Form
DSMB	Data Safety Monitoring Board
DMP	Data Management Plan

## ALLOB-DU1 - Clinical Study Protocol

ALLOB-DU1_CSP	V 05	Author: [name]	February 02, 2017	Pg. 18/136
---------------	------	-------------	-------------------	------------

DU	Delayed-union
EBV	Epstein-Bar Virus
EC	European Commission
ECs	Ethics Committees
EMA	European Medicines Agency
EPCs	Endothelial Progenitor Cells
EU	European Union
EudraCT	European Clinical Trials Database
FA	Full Analysis
GCP	Good Clinical Practice
GLP	Good Laboratory Practice
GMP	Good Manufacturing Practice
Gr.	Gram
HBV	Hepatitis B Virus
HCV	Hepatitis C Virus
HHV6	Human Herpes Virus Type 6
HIV	Human Immunodeficiency Virus
HSV-1	Herpes Simplex Virus Type 1
HTLV-1	Human T-lymphotropic Virus Type 1
IATA	International Air Transportation Association
IC/EC	Inclusion and Exclusion Criteria
ICF	Informed Consent Form
ICH	International Conference on Harmonization
IEC	Independent Ethics Committee
IMP	Investigational Medicinal Product
IMPD	Investigational Medicinal Product Dossier
IRB	Institutional Review Board
IRB	Institutional Review Board
LLOQ	Lower Limit of Quantification

